6.4.2. Analysis Methods

Descriptive statistics (mean, standard deviation, median and range) will be provided for the ECG parameters at each scheduled visit. Changes from baseline will be summarized by treatment group. Incidence of ECG parameters that meet criteria for abnormality will be tabulated for each treatment group.

A cross-tabulation of the worst abnormality versus baseline will be presented for the combination of analysis treatment- and follow-up phase and for the analysis treatment phase only. This table will also show the number (n) and percentage (%) of subjects per worst toxicity/abnormality, the number (n) and percentage (%) of subjects per emergent worst toxicity/abnormality.

A tabulation of the worst QT/QTc change versus baseline per treatment for the combination of analysis treatment- and follow-up phase will be presented and for the analysis treatment phase only.

Mean \pm SE graphs over time for the actual values and changes from baseline will be generated and presented by treatment group and by age group as assigned at Screening.

A listing of abnormal individual subject ECG values from scheduled and unscheduled timepoints will be provided. This listing will include all other timepoints for the corresponding subject/parameter. In addition, ECG: Overall interpretation will also be listed.

7. VIROLOGY

7.1. Definitions

Viral Strain Typing

The RSV subtype is determined at baseline using the RSV A/B qRT-PCR assay performed in the central laboratory.

Viral Sequencing

Viral resistance will be evaluated by next-generation sequencing (NGS) of the RSV Fusion (F) gene using a read frequency cut-off of 3%.

Baseline samples from all subjects will be sequenced to identify pre-existing genetic variations in the F gene. Post-baseline sequencing will be performed on the last evaluable on-treatment sample and/or during follow-up for all subjects (if viral load is high enough) to identify emerging amino acid substitutions in the F gene. Additional post-baseline sequencing can be performed on request of the sponsor virologist.

Genetic Variations

Genetic variations are defined as changes (on amino acid or nucleotide level) in the subject's virus's sequence compared to a reference sequence. Genetic variations can include substitutions, insertions and deletions. The reference sequences used will be RSV A Long strain (GenBank Accession number AY911262) for RSV A samples and RSV B strain 9320 (GenBank Accession number AY353550) for RSV B samples. Genetic variations will be reported on amino acid level.

- **Baseline genetic variation:** amino acid difference from the RSV A or RSV B reference strain detected at baseline with an NGS-read frequency $\geq 15\%$.

- **Emerging genetic variation:** a genetic variation (amino acid substitution, insertion or deletion) that is absent, i.e. an NGS-read frequency $<3\%$, at baseline but detected with an NGS-read frequency $\geq 15\%$ at a later post-baseline timepoint.
- **Enriched genetic variation:** a genetic variation (amino acid substitution, insertion or deletion) that is present at baseline with an NGS-read frequency $\geq 3\%$ and $<15\%$, but with an increase in NGS-read frequency of at least 15% post-baseline.
- **Genetic variation profile:** a specific genetic variation or combination of genetic variations at one or more timepoints.
- **RSV F-gene amino acid positions of interest:**
 - Short list of 8 F gene positions of interest for JNJ-53718678, based on *in vitro* selection experiments with JNJ-53718678 and/or *in vitro* reduced susceptibility to JNJ-53718678: positions 141, 143, 394, 398, 400, 486, 488 and 489
 - Long list of 24 F gene positions of interest for the class of RSV fusion inhibitors, based on *in vitro* selection experiments, clinical observations, and/or *in vitro* reduced susceptibility to RSV fusion inhibitors, as well as residues involved in binding of JNJ-53718678 to the RSV pre-fusion F protein: positions 127, 137, 138, 140, 141, 143, 144, 323, 338, 339, 392, 394, 396, 397, 398, 399, 400, 401, 474, 486, 487, 488, 489, and 517.

Analysis Timepoints

Virology results will be assigned to the visit windows as described in Sections 2.1.1 and 2.1.4. In addition to the timepoints corresponding to the visits at which samples for RSV F gene sequencing are collected, the below timepoints will be considered:

- Baseline: closest timepoint with sequencing data available prior to the first dose of study drug. Ideally, this will be the Day 1 pre-dose sample; however, if RSV F gene sequencing data cannot be obtained from this sample, the screening sample may be used for sequencing.
- Last Evaluable On-treatment Timepoint: last available post-baseline timepoint during the study treatment phase with sequencing data available. In case no On-Treatment assessment is available, the first assessment during study follow-up phase will be selected.
- Any Post-baseline Timepoint During the Study: all available post-baseline timepoints in the study with sequencing data available.

7.2. Analysis Methods

7.2.1. Viral Sequencing

Subjects with baseline RSV A+B co-infection will be excluded from the summary tables.

Baseline

The prevalence of baseline genetic variations in the RSV F gene (complete RSV F gene or considering the positions of interest), i.e. the number of subjects with baseline genetic variations in the RSV F gene, will be tabulated in frequency outputs (n, %).

Post-baseline

Emerging and enriched genetic variations in the RSV F gene (complete RSV F gene or considering the positions of interest) will be tabulated by analysis timepoint in frequency outputs (n, %).

Over the study period, amino acid changes from reference sequence at baseline and post-baseline will be listed for all subjects using an NGS-read frequency cut-off of 3%. For subjects with emerging or enriched genetic variations, RSV RNA viral load profiles including emerging or enriched genetic variations per timepoint, will be generated. Subgroup analyses by the presence of baseline genetic variations or emerging genetic variations will be tabulated to evaluate the impact on response (i.e. AUC_{Day 5} and time to **confirmed undetectable** RSV RNA viral load).

The aforementioned will be presented overall by treatment group and by the subgroups as defined in Section 2.4.

8. IMPACT OF PANDEMIC

With the onset of the global 2019 novel coronavirus (COVID-19) pandemic, impact on planned analyses is to be considered in accordance with regulatory guidance. Taking into consideration the study status, impact to subject safety, data quality and integrity is considered minimal.

With reference to the current version of the COVID-19 standard reporting – guiding principles, the following will be evaluated for COVID-19 impact and may be presented in a separate listing:

- Protocol deviations: deviations due to COVID-19 and can be considered major or minor.
- Treatment and study disposition: premature discontinuation of treatment/study due to COVID-19.
- Visit/assessment schedule: missed visits/assessments due to COVID-19.
- Adverse events: COVID-19 associated adverse events and deaths.

REFERENCES

ATTACHMENTS**ATTACHMENT 1: DIVISION OF MICROBIOLOGY AND INFECTIOUS DISEASES (DMID) PEDIATRIC TOXICITY TABLES (NOVEMBER 2007; DRAFT)****DIVISION OF MICROBIOLOGY AND INFECTIOUS DISEASES (DMID)
PEDIATRIC TOXICITY TABLES NOVEMBER 2007
DRAFT****ABBREVIATIONS:** Abbreviations utilized in the Table:

ULN = Upper Limit of Normal

LLN = Lower Limit of Normal

Rx = Therapy

Req = Required

Mod = Moderate

IV = Intravenous

ADL = Activities of Daily Living

Dec = Decreased

ESTIMATING SEVERITY GRADE

For abnormalities NOT found elsewhere in the toxicity tables use the scale below to estimate grade of severity:

GRADE 1	Mild: Transient or mild discomfort (<48 hours); no medical intervention/therapy required
GRADE 2	Moderate: Mild to moderate limitation in activity - some assistance may be needed; no or minimal medical intervention/therapy required
GRADE 3	Severe: Marked limitation in activity, some assistance usually required; medical intervention/therapy required, hospitalizations possible
GRADE 4	Life-threatening or death*: Extreme limitation in activity, significant assistance required; significant medical intervention/therapy required, hospitalization or hospice care probable

* The draft DMID pediatric toxicity tables characterize death as a Grade 5 event, for the purposes of this study the sponsor will categorize events into 4 grades and has included death with life-threatening in the Grade 4 category.

SERIOUS OR LIFE-THREATENING ADVERSE EVENTS

ANY clinical event deemed by the clinician to be serious or life-threatening should be considered a Grade 4 event. Clinical events considered to be serious or life-threatening include, but are not limited to: seizures, coma, tetany, diabetic ketoacidosis, disseminated intravascular coagulation, diffuse petechiae, paralysis, acute psychosis, severe depression.

COMMENTS REGARDING THE USE OF THESE TABLES

- Standardized and commonly used toxicity tables (Division of AIDS, NCI's Common Toxicity Criteria [CTC], and WHO) have been adapted for use by the DMID and modified to better meet the needs of participants in DMID trials.
- For parameters not included in the following toxicity tables, sites should refer to the “Guide For Estimating Severity Grade” located above.
- Criteria are generally grouped by body system.
- Some protocols may have additional protocol-specific grading criteria, which will supersede the use of these tables for specified criteria.

DIVISION OF MICROBIOLOGY AND INFECTIOUS DISEASES (DMID) PEDIATRIC TOXICITY TABLES NOVEMBER 2007

(Selected Values for children less than or equal to 3 months of age – does not apply to preterm infants)

For all parameters not listed in this table, please refer to the DMID Toxicity Table for children >3 months of age

HEMATOLOGY				
	Grade 1	Grade 2	Grade 3	Grade 4
Hemoglobin				
1-7 days old	13.0-14.0 g/dL	12.0-12.9 g/dL	<12 g/dL	Cardiac Failure secondary to Anemia
8-21 days old	12.0-13.0 g/dL	10.0-11.9 g/dL	<10.0 g/dL	Cardiac Failure secondary to Anemia
22-35 days old	9.5-10.5 g/dL	8.0-9.4 g/dL	<8.0 g/dL	Cardiac Failure secondary to Anemia
36-60 days old	8.5-9.4 g/dL	7.0-8.4 g/dL	<7.0 g/dL	Cardiac Failure secondary to Anemia
61-90 days old	9.0-9.9 g/dL	7.0-8.9 g/dL	<7.0 g/dL	Cardiac Failure secondary to Anemia
Absolute Neutrophil Count				
1 day old	5000-7000/mm ³	3000-4999/mm ³	1500-2999/mm ³	<1500/mm ³
2-6 days old	1750-2500/mm ³	1250-1749/mm ³	750-1249/mm ³	<750/mm ³
7-60 days old	1200-1800/mm ³	900-1199/mm ³	500-899/mm ³	<500/mm ³
61-90 days old	750-1200/mm ³	400-749/mm ³	250-399/mm ³	<250/mm ³

**DIVISION OF MICROBIOLOGY AND INFECTIOUS DISEASES (DMID)
PEDIATRIC TOXICITY TABLES NOVEMBER 2007**

(Selected values for children younger than or aged 3 months)

HEMATOLOGY (continued)				
	Grade 1	Grade 2	Grade 3	Grade 4
Bilirubin (fractionated bilirubin test must be performed when total bilirubin is elevated)				
<7 days old	-	20-25mg/dL	26-30 mg/dL	>30 mg/dL
7-60 days old	1.1-1.9xN	2.0-2.9xN	3.0-7.5xN	>7.5xN
61-90 days old	1.1-1.9xN	2.0-2.9xN	3.0-7.5xN	>7.5xN
Creatinine				
<7 days old	1.0-1.7 mg/dL	1.8-2.4 mg/dL	2.5-3.0 mg/dL	>3.0 mg/dL
7-60 days old	0.5-0.9 mg/dL	1.0-1.4 mg/dL	1.5-2.0 mg/dL	>2.0 mg/dL
61-90 days old	0.6-0.8 mg/dL	0.9-1.1 mg/dL	1.2-1.5 mg/dL	>1.5 mg/dL
Creatinine Clearance				
<7 days old	35-40 mL/min	30-34 mL/min	25-29 mL/min	<25 mL/min
7-60 days old	45-50 mL/min	40-44 mL/min	35-39 mL/min	<35 mL/min
61-90 days old	60-75 mL/min	50-59 mL/min	35-49 mL/min	<35 mL/min
Hypocalcemia				
<7 days old	6.5-6.9 mEq/L	6.0-6.4 mEq/L	5.5-5.9 mEq/L	<5.5 mEq/L
7-60 days old	7.6-8.0 mEq/L	7.0-7.5 mEq/L	6.0-6.9 mEq/L	<6.0 mEq/L
61-90 days old	7.8-8.4 mEq/L	7.0-7.7 mEq/L	6.0-6.9 mEq/L	<6.0 mEq/L
Hypercalcemia				
<7 days old	12.0-12.4 mEq/L	12.5-12.9 mEq/L	13.0-13.5 mEq/L	>13.5 mEq/L
7-60 days old	10.5-11.2 mEq/L	11.3-11.9 mEq/L	12.0-13.0 mEq/L	>13.0 mEq/L
61-90 days old	10.5-11.2 mEq/L	11.3-11.9 mEq/L	12.0-13.0 mEq/L	>13.0 mEq/L

**DIVISION OF MICROBIOLOGY AND INFECTIOUS DISEASES (DMID)
PEDIATRIC TOXICITY TABLES NOVEMBER 2007**

(Older than 3 months of age)

LOCAL REACTIONS				
	Grade 1	Grade 2	Grade 3	Grade 4
Induration	<10 mm	10-25 mm	26-50 mm	>50 mm
Erythema	<10 mm	10-25 mm	26-50 mm	>50 mm
Edema	<10 mm	10-25 mm	26-50 mm	>50 mm
Rash at Injection Site	<10 mm	10-25 mm	26-50 mm	>50 mm
Pruritus	Slight itching at injection site	Moderate itching at injection extremity	Itching at injection extremity and other sites	Itching over entire body

HEMATOLOGY				
	Grade 1	Grade 2	Grade 3	Grade 4
Hemoglobin for children older than 3 months and younger than 2 years of age	9.0 - 9.9 g/dL	7.0 - 8.9 g/dL	<7.0 g/dL	Cardiac Failure secondary to anemia
Hemoglobin for children older than 2 years of age	10 - 10.9 g/dL	7.0 - 9.9 g/dL	<7.0 g/dL	Cardiac Failure secondary to anemia
Absolute Neutrophil Count	750 - 1200/mm ³	400 - 749/mm ³	250 - 399/mm ³	<250/mm ³
Platelets	-----	50,000 - 75,000/mm ³	25,000 - 49,999/mm ³	<25,000/mm ³
Prothrombin Time (PT)	1.1 - 1.2 x ULN	1.3 - 1.5 x ULN	1.6 - 3.0 x ULN	>3.0 x ULN
Partial Thromboplastin Time (PTT)	1.1 - 1.6 x ULN	1.7 - 2.3 x ULN	2.4 - 3.0 x ULN	>3.0 x ULN

**DIVISION OF MICROBIOLOGY AND INFECTIOUS DISEASES (DMID)
PEDIATRIC TOXICITY TABLES NOVEMBER 2007**

(Older than 3 months of age)

GASTROINTESTINAL				
	Grade 1	Grade 2	Grade 3	Grade 4
Bilirubin (when accompanied by any increase in other liver function test)	1.1 - <1.25 x ULN	1.25 - <1.5 x ULN	1.5 - 1.75 x ULN	>1.75 x ULN
Bilirubin (when other liver function are in the normal range)	1.1 - <1.5 x ULN	1.5 - <2.0 x ULN	2.0 - 3.0 x ULN	>3.0 x ULN

AST (SGOT)	1.1 - <2.0 x ULN	2.0 - <3.0 x ULN	3.0 - 8.0 x ULN	>8 x ULN
ALT (SGPT)	1.1 - <2.0 x ULN	2.0 - <3.0 x ULN	3.0 - 8.0 x ULN	>8 x ULN
GGT	1.1 - <2.0 x ULN	2.0 - <3.0 x ULN	3.0 - 8.0 x ULN	>8 x ULN
Pancreatic Amylase	1.1 - 1.4 x ULN	1.5 - 1.9 x ULN	2.0 - 3.0 x ULN	>3.0 x ULN
Uric Acid	7.5 - 9.9 mg/dL	10 - 12.4 mg/dL	12.5 - 15.0 mg/dL	>15.0 mg/dL
CPK	See Neuromuscular Toxicity			
Appetite	-	Decreased appetite	Appetite very decreased, no solid food taken	No solid or liquid taken
Abdominal Pain	Mild	Moderate- No Treatment Needed	Moderate- Treatment Needed	Severe- Hospitalized for treatment
Diarrhea	Slight change in consistency and/or frequency of stools	Liquid stools	Liquid stools greater than 4x the amount or number normal for this child	Liquid stools greater than 8x the amount or number normal for this child

**DIVISION OF MICROBIOLOGY AND INFECTIOUS DISEASES (DMID)
PEDIATRIC TOXICITY TABLES NOVEMBER 2007**

(Older than 3 months of age)

GASTROINTESTINAL (continued)				
	Grade 1	Grade 2	Grade 3	Grade 4
Constipation	Slight change in the consistency/frequency of stool	Hard, dry stools with a change in frequency	Abdominal pain	Distention and Vomiting
Nausea	Mild	Moderate- Decreased oral intake	Severe-Little oral intake	Unable to ingest food or fluid for more than 24 hours
Vomiting	1 episode/day	2-3 episodes per day	4-6 episodes per day	Greater than 6 episodes per day or Intractable Vomiting

**DIVISION OF MICROBIOLOGY AND INFECTIOUS DISEASES (DMID)
PEDIATRIC TOXICITY TABLES NOVEMBER 2007**

(Older than 3 months of age)

ELECTROLYTES				
	Grade 1	Grade 2	Grade 3	Grade 4
CREATININE				
3 months - 2 years of age	0.6 - 0.8 x ULN	0.9 - 1.1 x ULN	1.2 - 1.5 x ULN	>1.5 x ULN
2 years - 12 years of age	0.7 - 1.0 x ULN	1.1 - 1.6 x ULN	1.7 - 2.0 x ULN	>2.0 x ULN
Older than 12 years of age	1.0 - 1.7 x ULN	1.8 - 2.4 x ULN	2.5 - 3.5 x ULN	>3.5 x ULN
Hypernatremia	-	<145 - 149 mEq/L	150 - 155 mEq/L	>155 mEq/L or abnormal sodium AND mental status changes
Hyponatremia	-	130 - 135 mEq/L	129 - 124 mEq/L	<124 mEq/L or abnormal sodium AND mental status changes
Hyperkalemia	5.0 - 5.9 mEq/L	6.0 - 6.4 mEq/L	6.5 - 7.0 mEq/L	>7.0 mEq/L or abnormal potassium AND cardiac arrhythmia
Hypokalemia	3.0-3.5 mEq/L	2.5-2.9 mEq/L	2.0-2.4 mEq/L	<2.0 mEq/L or abnormal potassium AND cardiac arrhythmia
Hypercalcemia	10.5 - 11.2mg/dL	11.3 - 11.9 mg/dL	12.0 - 12.9 mg/dL	>13.0 mg/dL
Hypocalcemia	7.8 - 8.4 mg/dL	7.0 - 7.7 mg/dL	6.0 - 6.9 mg/dL	<6.0 mg/dL
Hypomagnesemia	1.2 - 1.4 mEq/L	0.9 - 1.1 mEq/L	0.6 - 0.8 mEq/L	<0.6 mEq/L or abnormal magnesium AND cardiac arrhythmia
Hypoglycemia	55 - 65 mg/dL	40 - 54 mg/dL	30 - 39 mg/dL	<30 mg/dL or abnormal glucose AND mental status changes
Hyperglycemia	116 - 159 mg/dL	160 - 249 mg/dL	250 - 400 mg/dL	>400 mg/dL or ketoacidosis
Proteinuria	Tr-1+ or <150 mg/day	2+ or 150-499 mg/day	3+ or 500-1000 mg/day	4+ or Nephrotic syndrome >1000 mg/day

**DIVISION OF MICROBIOLOGY AND INFECTIOUS DISEASES (DMID)
PEDIATRIC TOXICITY TABLES NOVEMBER 2007**

(Older than 3 months of age)

ELECTROLYTES (continued)				
	Grade 1	Grade 2	Grade 3	Grade 4
Hematuria	Microscopic <25 cells/hpf	Microscopic >25 cells/hpf	----	Gross hematuria
Hypernatremia	-	<145 - 149 mEq/L	150 - 155 mEq/L	>155 mEq/L or abnormal sodium AND mental status changes
Hyponatremia	-	130 - 135 mEq/L	129 - 124 mEq/L	<124 mEq/L or abnormal sodium AND mental status changes
Hyperkalemia	5.0 - 5.9 mEq/L	6.0 - 6.4 mEq/L	6.5 - 7.0 mEq/L	>7.0 mEq/L or abnormal potassium AND cardiac arrhythmia
Hypokalemia	3.0 – 3.5 mEq/L	2.5 - 2.9 mEq/L	2.0 - 2.4 mEq/L	<2.0 mEq/L or abnormal potassium AND cardiac arrhythmia
Hypercalcemia	10.5 - 11.2mg/dL	11.3 - 11.9 mg/dL	12.0 - 12.9 mg/dL	>13.0 mg/dL
Hypocalcemia	7.8 - 8.4 mg/dL	7.0 - 7.7 mg/dL	6.0 - 6.9 mg/dL	<6.0 mg/dL
Hypomagnesemia	1.2 - 1.4 mEq/L	0.9 - 1.1 mEq/L	0.6 - 0.8 mEq/L	<0.6 mEq/L or abnormal magnesium AND cardiac arrhythmia
Hypoglycemia	55 - 65 mg/dL	40 - 54 mg/dL	30 - 39 mg/dL	<30 mg/dL or abnormal glucose AND mental status changes
Hyperglycemia	116 - 159 mg/dL	160 - 249 mg/dL	250 - 400 mg/dL	>400 mg/dL or ketoacidosis
Proteinuria	Tr-1+ or <150 mg/day	2+ or 150-499 mg/day	3+ or 500- 1000 mg/day	4+ or Nephrotic syndrome >1000 mg/day
Hematuria	Microscopic <25 cells/hpf	Microscopic >25 cells/hpf	-	Gross hematuria

**DIVISION OF MICROBIOLOGY AND INFECTIOUS DISEASES (DMID)
PEDIATRIC TOXICITY TABLES NOVEMBER 2007**

(Older than 3 months of age)

CENTRAL NERVOUS SYSTEM (CNS)				
	Grade 1	Grade 2	Grade 3	Grade 4
Generalized CNS Symptoms	-	-	Dizziness	Hypotonic, hyporesponsive episodes; Seizures; Apnea/Bradycardia; Inconsolable crying >3 hrs;
Headache	Mild	Moderate, Responds to non-narcotic analgesia	Moderate to Severe, Responds to narcotic analgesia	Intractable
Level of Activity	-	Slightly irritable OR slightly subdued	Very irritable OR Lethargic	Inconsolable OR Obtunded
Visual	-	Blurriness, diplopia, or horizontal nystagmus of <1 hour duration, with spontaneous resolution	More than 1 episode of Grade 2 symptoms per week, or an episode of Grade 2 symptoms lasting more than 1 hour with spontaneous resolution by 4 hours or vertical nystagmus	Decrease in visual acuity, visual field deficit, or oculogyric crisis
Myelopathy	-	None	None	Myelopathic/spinal cord symptoms, such as: pyramidal tract weakness and disinhibition, sensory level, loss of proprioception, bladder/bowel dysfunction

**DIVISION OF MICROBIOLOGY AND INFECTIOUS DISEASES (DMID)
PEDIATRIC TOXICITY TABLES NOVEMBER 2007**

(Older than 3 months of age)

PERIPHERAL NERVOUS SYSTEM				
	Grade 1	Grade 2	Grade 3	Grade 4

Neuropathy/ Lower Motor Neuropathy	-	Mild transient Paresthesia only	Persistent or progressive paresthesias, burning sensation in feet, or mild dysesthesia; no weakness; mild to moderate deep tendon reflex changes; no sensory loss	Onset of significant weakness, decrease or loss of DTRs, sensory loss in "stocking glove" distribution, radicular sensory loss, multiple cranial nerve involvement; bladder or bowel dysfunction, fasciculations, respiratory embarrassment from chest wall weakness.
Myopathy or Neuromuscular Junction Impairment	Normal or mild (<2 x ULN) CPK elevation	Mild proximal weakness and/or atrophy not affecting gross motor function. Mild myalgias, +/- mild CPK elevation (<2 x ULN)	Proximal muscle weakness and/or atrophy affecting motor function +/- CPK elevation; or severe myalgias with CPK >2 x ULN;	Onset of myasthenia-like symptoms (fatigable weakness with external, variable ophthalmoplegia and/or ptosis), or neuromuscular junction blockade (acute paralysis) symptoms

**DIVISION OF MICROBIOLOGY AND INFECTIOUS DISEASES (DMID)
PEDIATRIC TOXICITY TABLES NOVEMBER 2007**

[figure not shown]
(Older than 3 months of age)

OTHER				
	Grade 1	Grade 2	Grade 3	Grade 4
Allergy	Pruritus without Rash	Pruritic Rash	Mild Urticaria	Severe Urticaria Anaphylaxis, Angioedema
Drug Fever (Rectal)	-	38.5 - 40.0°C 101.3 – 104.0 °F	Greater than 40.0°C Greater than 104.0°F	Sustained Fever: Equal or greater than 40.0°C (104.0°F) for longer than 5 days
Cutaneous	Localized rash	Diffuse maculopapular Rash	Generalized urticaria	Stevens-Johnson Syndrome or Erythema multiforme

[figure not shown]
Stomatitis	Mild discomfort	Painful, difficulty swallowing, but able to eat and drink	Painful: unable to swallow solids	Painful: unable to swallow liquids; requires IV fluids
Clinical symptoms not otherwise specified in this table	No therapy; monitor condition	May require minimal intervention and monitoring	Requires medical care and possible hospitalization	Requires active medical intervention, hospitalization, or hospice care
Laboratory values not otherwise specified in this table	Abnormal, but requiring no immediate intervention; follow	Sufficiently abnormal to require evaluation as to causality and perhaps mild therapeutic intervention, but not of sufficient severity to warrant immediate changes in study drug	Sufficiently severe to require evaluation and treatment, including at least temporary suspension of study drug	Life-threatening severity; Requires immediate evaluation, treatment, and usually hospitalization; Study drug must be stopped immediately and should not be restarted until the abnormality is clearly felt to be caused by some other mechanism that study drug

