6.2. Clinical Laboratory Tests

6.2.1. Definitions

Laboratory parameters of hematology, serum chemistry, and urinalysis will be investigated. Analyses will be based on International System of Units (SI) converted values as available in the database.

Toxicity grades and abnormalities for laboratory parameters

The laboratory abnormalities will be determined according to the Division of Microbiology and Infectious Diseases (DMID) pediatric toxicity tables (see [Attachment 1](#)). Toxicity grades where available per parameter and age group, will be provided by the central laboratory and will be used in the analysis. In case no DMID toxicity grades are defined for a test and/or age group, the abnormalities (above/below normal range) will be used.

In determining toxicity grades/abnormalities for each subject the following rules are applied:

- Worst grades/abnormalities are determined over the whole observational period, per phase (analysis treatment, analysis follow-up [separately] and in combination analysis treatment + follow-up phase), including scheduled and unscheduled measurements.
- The abnormalities "abnormally low" and "abnormally high" are considered equally important, i.e. if a subject has as well an abnormally low as an abnormally high value post-baseline, both abnormalities are shown in the tables. This means that the sum of the percentages can be more than 100%.

- If, for a specific test, the grading list provides distinct limits for abnormally low (=hypo) values as well as for abnormally high (=hyper) values, this test should be repeated for hyper- and hypo- limits separately in cross-tabulations.

For subjects enrolled under original protocol dated 13 July 2018, coagulation function will be monitored during this clinical study through evaluation of partial thromboplastin time (PTT) and activated partial thromboplastin time (aPTT) in seconds, and calculation of the International normalized ratio by the central lab. Grading of abnormalities in these parameters (PT and PTT) will be based on the DMID Pediatric Toxicity Table (see [Attachment 1](#)). Coagulation will not be evaluated in subjects enrolled as of protocol amendment 1 (dated 14 May 2019).

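### Attachment 1 prints creatinine and calcium cut-offs in inconsistent units, so the grading standard named in Section 6.2.1 gives toxicity grades to values that are not abnormal

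*SAP*

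**What the plan says.** Section 6.2.1 of the SAP sets the grading rule: "The laboratory abnormalities will be determined according to the" DMID pediatric toxicity tables, reproduced as Attachment 1. The central laboratory supplies the grades for tests and age groups that have them, and the analysis uses those grades. Where the tables define no grade for a test or age group, flags above or below the normal range are used instead. Analyses use SI-converted values.

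The abbreviations in Attachment 1 state "ULN = Upper Limit of Normal". The rows at issue are:

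- Creatinine, in the table for children older than 3 months: "3 months - 2 years of age 0.6 - 0.8 x ULN 0.9 - 1.1 x ULN 1.2 - 1.5 x ULN", with Grade 4 above 1.5 x ULN. The next row begins "2 years - 12 years of age 0.7 - 1.0 x ULN 1.1 - 1.6 x ULN".
- Creatinine, in the table for children up to 3 months: "61-90 days old 0.6-0.8 mg/dL 0.9-1.1 mg/dL 1.2-1.5 mg/dL >1.5 mg/dL".
- Hypocalcemia, in the table up to 3 months: "61-90 days old 7.8-8.4 mEq/L 7.0-7.7 mEq/L 6.0-6.9 mEq/L <6.0 mEq/L".
- Hypocalcemia, in the table for older children: "Hypocalcemia 7.8 - 8.4 mg/dL 7.0 - 7.7 mg/dL 6.0 - 6.9 mg/dL <6.0 mg/dL".

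Under Section 6.2.2 the grades feed the cross-tabulation of worst against baseline grade, the emergent and cumulative counts, and a separate listing of results at Grade 2 or above.

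**The concern.** A toxicity grade on a multiple-of-ULN scale should begin above 1.0. The creatinine rows for children over 3 months begin at 0.6 and 0.7, so part of the normal range is graded as toxic. The calcium rows carry the same cut-offs under two units that differ by a factor of about two, so the two tables cannot both be right.

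If the printed rows are applied, creatinine movement within the normal range can produce emergent Grade 1 or 2 results, and those at Grade 2 enter the separate listing. The normal-range fallback in Section 6.2.1 does not help, because it applies only where no grade is defined; here a grade is defined, but doubtful.

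**Working it through.** The plan has no computed figure to reproduce. The check applies the printed rows and converts one unit.

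**Creatinine, 3 months to 2 years** (inputs: Attachment 1, Electrolytes table, and its definition of ULN)

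| Result as a multiple of ULN | Grade as printed | Above ULN? |
|---|---|---|
| 0.5 | none | no |
| 0.6, 0.7, 0.8 | 1 | no |
| 0.9, 1.0 | 2 | no |
| 1.1 | 2 | yes |
| 1.2 to 1.5 | 3 | yes |
| 1.6 | 4 | yes |

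All of Grade 1, and Grade 2 from 0.9 to 1.0, lies at or below ULN. In the 2-12-year row, which covers subjects over 2 years of age, the whole of Grade 1 (0.7 to 1.0 x ULN) does too.

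Two comparisons within Attachment 1 suggest that the unit, not the numbers, is at fault:

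- The 61-90-day creatinine row has the same four steps (0.6-0.8, 0.9-1.1, 1.2-1.5, above 1.5) in mg/dL.
- AST, ALT and GGT, in the Gastrointestinal table for the same ages, are also graded in multiples of ULN but start above it: "1.1 - <2.0 x ULN 2.0 - <3.0 x ULN 3.0 - 8.0 x ULN >8 x ULN".

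**Calcium**

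Inputs from Attachment 1:
- Older than 3 months: Grade 1 hypocalcemia ends at 8.4 mg/dL and Grade 1 hypercalcemia starts at 10.5 mg/dL. The ungraded band is therefore 8.5 to 10.4 mg/dL.
- 7-60 and 61-90 days: Grade 4 hypocalcemia is below 6.0 mEq/L in both rows.

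Input from outside the documents: calcium has atomic weight 40.078 and valence 2. This is a physical constant.

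1. Conversion: 1 mEq/L = 40.078 / 2 / 10 = 2.004 mg/dL.
2. Ungraded band: 8.5 / 2.004 = 4.24 mEq/L and 10.4 / 2.004 = 5.19 mEq/L. Rounding the factor to 2 gives 4.25 to 5.20.
3. Both ends are below 6.0 mEq/L, so the whole band is Grade 4 at 7-90 days.
4. If the 7-60-day row's own numbers are read as mg/dL, its ungraded band starts at 8.1 mg/dL. 8.1 / 2.004 = 4.04 mEq/L, and the band is still all Grade 4.
5. In reverse, 6.0 x 2.004 = 12.0 mg/dL, which the older table calls Grade 3 hypercalcemia.
6. At the other end, Grade 1 hypercalcemia at 61-90 days starts at 10.5 mEq/L, and 10.5 x 2.004 = 21.0 mg/dL. The older table already assigns Grade 4 above 13.0 mg/dL.

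The numeric match between the two calcium tables is exact for hypocalcemia at 61-90 days. The 7-60-day row differs slightly in Grades 1 and 2 but has the same Grade 4 limit.

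**If the units are aligned.** With creatinine at 3 months to 2 years in mg/dL, that row and the 61-90-day row coincide. With calcium up to 3 months in mg/dL, the ungraded bands become 8.1-10.4 (7-60 days) and 8.5-10.4 (61-90 days).

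**The case against.** The strongest objection is that the SAP does not derive grades from Attachment 1. Section 6.2.1 has the central laboratory supply them, and analysis on SI-converted values implies a unit mapping outside this document. The laboratory may be using correct units. This stands, and it makes any effect on the output conditional. It does not clear the attachment, which is the only grading standard the SAP names; a laboratory using other units would depart from it without a record.

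Attachment 1 also reproduces an external draft table, in which the sponsor's one flagged change is where death is graded. A reader might infer that the sponsor mistranscribed the units. The documents cannot show whether the fault is in the source or in the copy.

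A reader might also infer that every infant up to 3 months will show Grade 4 hypocalcemia. The documents do not support this. The SAP does not say that calcium is measured, the laboratory's units are unknown, and the table for that age excludes preterm infants. The lower Grade 4 limit of 5.5 mEq/L belongs to the under-7-day row and is irrelevant to a trial that enrolls from 28 days.

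Finally, a reader might infer that a renal signal would be lost. Misgrading would fall on all arms, including placebo. Emergent means worse than baseline. Section 6.2.2 also provides continuous summaries and changes from baseline, and the central laboratory reports eGFR. Dilution of a signal is the most that can be claimed.

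**Conclusion.** Attachment 1 is wrong as printed for creatinine in children over 3 months and, if calcium is measured, for calcium in infants up to 3 months. The creatinine part needs no outside figure. That creatinine is measured is inferred from the eGFR by the Schwarz formula in Section 6.2.1. The calcium part rests on the unit conversion and on calcium being on the panel.

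On the printed scale, grading starts at 0.6 x ULN instead of above ULN, with Grade 2 from 0.9 x ULN. This describes the scale: the span from 0.6 to 1.0 x ULN must not be read as 40% of subjects, since the SAP gives no creatinine distribution and no count for the age band.

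If the laboratory applies the printed units, false Grade 1 and 2 creatinine results enter the worst-grade and emergent-grade tables, and the Grade 2 results enter the separate listing, in all arms. If it does not, the fault is confined to documentation. Safety is summarized descriptively without formal testing (Section 6), and the primary efficacy analysis is unaffected. The correction should still be made, because followed as written the rule gives wrong grades.

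**What to change.** Before database lock:

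1. Reconcile the creatinine and calcium units across the age rows of Attachment 1 and with the central laboratory's grading specification.
2. Correct the attachment, or add a footnote giving the units that apply.
3. Confirm in writing that the supplied grades used the reconciled units. If they did not, have the laboratory regrade those parameters.
4. For any row that cannot be confirmed, amend Section 6.2.1 so that flags above or below the normal range replace its grades. This would be a new rule, because the present fallback covers only tests or age groups with no grade defined.

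The cost is a short correction and one exchange with the laboratory, plus regrading of at most two parameters if the printed units were used.
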